12.8.4.1. Reporting Process

UPs posing risks to subjects or others as noted above will be reported to local IRB using a Medwatch or CIOMS report of the event (including a description of the event with information regarding its fulfillment of the above criteria, follow-up/resolution and need for revision to consent form and/or other study documentation) will be completed.

All Serious Adverse Events, regardless of causal relationship to the investigational product, will be forwarded to **Merck Worldwide Product Safety** via fax (**[contact]**) within 2 working days of the investigator becoming aware of the event and no later than 3 calendar days.

The Principal Investigator is expected to provide as much of the following information:

- Protocol name and number
- Subject identifiers (no PHI will be shared with the IRB, unless requested)
- Demographic data
- Nature of the event
- Severity of the event
- Probable relationship (causality) of AE to study procedure
- Date and time of AE onset
- Date and time of AE resolution, if available
- Concomitant medications that the participant was taking for an underlying medical condition or disease and the therapeutic agents used for the treatment of the adverse event
 - Clinical assessment of participant conducted at time of SAE/AE
 - Results of any laboratory and/or diagnostic procedures, and treatment
 - Follow-up plan
 - Outcome
 - Autopsy findings (if appropriate)

The Principal Investigator will provide details about the AE/ADE as they become available. If additional information cannot be obtained for whatever reason, this will be documented. The Principal Investigator should inform the IRB when no other information is expected. The Principal Investigator should provide the IRB with a logical, complete, and accurate narrative description of the SAE based upon the above information.

The Principal Investigator should promptly determine an assessment of causality

The IRB determines if any corrective actions should be initiated as a result of any known specific or collective SAE/AE(s) and inform the principal investigator of the corrective action (e.g., revision of informed consent form, protocol, CRF).

The Principal Investigator/designee should keep originals or photocopies of all relevant documentation, including facsimile confirmations, and file them in the participant's file.

The Principal Investigator should ensure that all routine AE(s) are reported as part of the periodic or annual reporting requirements to the IRB of record.

The Principal Investigator should file copies of all correspondence with the IRB in the appropriate section of the Regulatory Master File or site study file.

Other Reportable Events:

The following events are also reportable to the IRB:

- Any adverse experience that, even without detailed analysis, represents an unexpected SAE that is rare in the absence of drug exposure (such as agranulocytosis, hepatic necrosis).
- Any AE that would cause a modification to the investigators brochure, protocol or ICF, or would prompt other action by the IRB to assure protection of human subjects.

- Information that indicates a change to the risks or potential benefits of the research, in terms of severity or frequency. For example:
 - An interim analysis indicates that participants have a lower rate of response to treatment than initially expected.
 - Safety monitoring indicates that a particular side effect is more severe, or more frequent than initially expected.
 - A paper is published from another study that shows that an arm of your research study is of no therapeutic value.
- Breach of confidentiality
- Change to the protocol taken without prior IRB review to eliminate apparent immediate hazard to a research participant.
- Incarceration of a participant when the research was not previously approved under Subpart C and the investigator believes it is in the best interest of the subject to remain on the study.
- Complaint of a participant when the complaint indicates unexpected risks or the complaint cannot be resolved by the research team.
- Protocol violation (meaning an accidental or unintentional deviation from the IRB approved protocol) that in the opinion of the investigator placed one or more participants at increased risk, or affects the rights or welfare of subjects.

Unanticipated Problem Involving Risks to Subjects or Others (UPRSO): Any incident, experience, or outcome that meets **all** of the following criteria:

- 1) Unexpected (in terms of nature, severity, or frequency) given a) the research procedures that are described in the protocol-related documents, such as the IRB-approved research protocol, informed consent document, or investigators brochure; and b) the characteristics of the subject population being studied;
- 2) Related or possibly related to participation in the research (possibly related to participation in the research means there is a reasonable possibility that the AE, experience, or outcome may have been caused by the procedures involved in the research.); and
- 3) Suggests that the research places subjects or others at a greater risk of harm (including physical, psychological, economic, or social harm) than was previously known or recognized.

12.9. Subject Withdrawal

A subject has the right to withdraw from the study entirely at any time for any reason without prejudice to future medical care by the investigator or other physician. The investigator also has the right to withdraw subjects from the study in the event of concurrent illness, AEs, or other reasons deemed to be in the subject's best interest.

Subjects **must be withdrawn** from the trial (treatment and procedures) for the following reasons:

- Subject withdraws consent for study treatment and study procedures. A subject must be removed from the trial at his/her own request or at the request of his/her legally acceptable representative. At any time during the trial and without giving reasons, a subject may decline to participate further. The subject will not suffer any disadvantage as a result.

- Subject becomes pregnant while undergoing treatment with Zepatier—therapy will be stopped as there are no human safety data of Zepatier during pregnancy. There are no adequate and well-controlled studies with Zepatier in pregnant women. No effects on embryo-fetal development were observed in rats or rabbits at grazoprevir or elbasvir exposures higher than exposures in humans at the recommended clinical dose. Because animal reproduction studies are not always predictive of human response, Zepatier should be used during pregnancy only if the potential benefit justifies the potential risk to the fetus. Because the transmission rates of HCV from mother to fetus are very small, and HCV can be treated after pregnancy and delivery, therapy will not be continued during pregnancy. Patients will continue with the regularly scheduled study visits, but will not be eligible to receive continued Zepatier therapy.
- Zepatier is no longer produced by the company, or if a decision is made to stop the study patients will not receive study drug, but will continue with study visits as scheduled.
- Subject becomes pregnant while undergoing treatment with Epclusa—therapy will be stopped.
- Epclusa is no longer produced by the manufacturer, or if a decision is made to stop the study patients will not receive study drug, but will continue with study visits as scheduled.

Subject develops a condition that it is life threatening or any other significant risk as judged by the Investigators. Patients will not receive study drug, but will continue with study visits as scheduled. Any subject removed from the trial will remain under medical supervision until discharge or transfer is medically acceptable.

In all cases, the reason for withdrawal must be recorded in the CRF and in the subject's medical records.

In order to preserve the integrity of the intention-to-treat analysis, even if the subject is withdrawn from the treatment portion of the protocol (either due to subject, physician, or investigator decision), it is imperative to continue with the scheduled follow-up assessments both for the safety of the subject and for completeness of data collection. This will be explained to potential subjects at the time of informed consent. The importance of adherence with study visits will be reinforced throughout the trial. If the treatment is permanently withdrawn, the subject will return to the center for safety assessment (history, physical examination, and clinical laboratories, if necessary).

12.10. Confidentiality of Study Data

Information about study subjects will be kept confidential and managed according to the requirements of the Health Insurance Portability and Accountability Act of 1996 (HIPAA). Those regulations require a signed subject authorization informing the subject of the following:

- What protected health information (PHI) will be collected from subjects in this study
- Who will have access to that information and why
- Who will use or disclose that information
- The rights of a research subject to revoke their authorization for use of their PHI

In the event that a subject revokes authorization to collect or use PHI, the investigator, by regulation, retains the ability to use all information collected prior to the revocation of subject authorization. For subjects that have revoked authorization to collect or use PHI, attempts should be made to obtain permission to collect at least vital status (i.e., that the subject is alive) at the end of their scheduled study period.

Should direct access to medical records require a waiver or authorization separate from the subject's statement of informed consent, it is the responsibility of the Investigator to obtain such permission in writing from the appropriate individual.

12.11. Potential Risks

12.11.1. Risks of Study Procedures

There are several areas of potential risk in this study. We will obtain several blood samples from each subject. There is a risk of bruising, hematoma, and infection after phlebotomy, which are possible but not considered serious AEs. Fainting may occur, which is unlikely but considered a serious AE. The removal of <70 cc of blood every 1-4 weeks during the 40-week post-transplant period is a potential risk; however this amount is routinely taken from subjects for clinical indications without adverse effect. Study medications will be delayed until after phlebotomy on each study day.

Because we may store subjects' blood samples, there may be confidentiality risks associated with the storage and analysis of those samples or the information resulting from the analysis of those samples. Samples may be used for genetic testing. Under some circumstances, it can be a risk for genetic information to be known. To help ensure confidentiality, samples will be coded and stored in a secured facility. While situations cannot be foreseen where potentially sensitive genetic information is revealed or where people who should not have this information could obtain it (representing a loss of confidentiality), however, it is possible that presently unforeseen situations may arise where this could happen.

The risk of undergoing screening includes potential identification of new health problems that subjects were unaware of. If we discover new health problems, we will answer subjects' questions and try to arrange appropriate treatment if any is needed. If new health problems are discovered, it is possible that subjects would not be able to enter this study. It is also possible that subjects would no longer be eligible for lung transplantation based on the results.

The risks of lung transplant surgery include blood loss, infections, and deep vein thrombosis. There are also risks related to immunosuppression and standard anti-infective therapy.

The risks of any transplant include primary graft non-function, delayed graft function, acute rejection, and death. Re-admissions within 30 days after a lung transplant are expected in approximately 40% of patients.

There may also be a small risk of developing Focal and Segmental Glomerulosclerosis (FSGS) after receiving a lung from a HCV positive donor. However, this condition can also develop in patients who do not have HCV. After transplant, we will monitor all patients for FSGS and similar conditions.

12.11.2. Risk of Genotyping Failure

There is a risk of failure of the Genotyping LDT in that no result is obtained. In that case, the investigators will use their judgment to select the most appropriate empirical treatment regimen.

There is also a risk of the Genotyping LDT giving an incorrect genotype. The risk to the recipient participant, in this event, is that they receive the transplant, but are possibly unable to be adequately treated for HCV positivity. Failure of the LDT to give an accurate genotype could be due to a mixed infection (e.g. genotype 1 and 2) or HCV genotype 4f infection in the donor sample.

12.11.3. Risk of NS5a Drug Resistance Test Failure

The potential risks of the NS5a resistance testing are false negative and false positive test results. The risk of a false negative test result would be if the test does not report any one of the four pertinent polymorphisms, even though they are present (the presence of which would be rare). In this case, the patient would receive only 12 weeks of Zepatier (rather than 16 weeks of Zepatier + renal-dosed Ribavirin), and potentially fail first-line therapy, requiring second-line therapy.

A false positive result is less likely to happen than a false negative result. The risk of a false positive test result would be if the test reports a polymorphism when the subject does not have one. Hence, the subject would be exposed to Zepatier for 4 weeks longer than needed as well as Ribavirin, and potentially experiencing the products' side effects.

12.11.4. Risk of Study Drugs

Zepatier

In subjects receiving Zepatier for 12 weeks, the most commonly reported adverse reactions of all intensity (greater than or equal to 5% in placebo-controlled trials) were fatigue, headache, and nausea. In subjects receiving Zepatier with ribavirin for 16 weeks, the most commonly reported adverse reactions of moderate or severe intensity (greater than or equal to 5%) were anemia and headache.¹⁶⁻¹⁸ The greatest risk is failure to achieve SVR12 after treatment with Zepatier, leading to chronic HCV.

There is a risk of fetal harm and birth defects should any woman taking Zepatier become pregnant while on the drug.¹⁶⁻¹⁸ Due to the age of the participants, this is a small risk, as all will be over 40 and unlikely to become pregnant. However, to mitigate this risk, all pre-menopausal women with a uterus will be screened for pregnancy before enrollment and instructed to use a highly effective form of birth control (e.g. abstinence, intrauterine device, etc.). Highly effective forms of birth control will be defined by the Mycophenolate Risk Evaluation and Mitigation Strategy (REMS), a standard protocol used for post-transplant patients at Penn being treated with Mycophenolate.

Sovaldi (Sofosbuvir)

The most common adverse events (incidence greater than or equal to 20%, all grades) observed with Sovaldi in combination with ribavirin were fatigue and headache. The most common adverse events observed with Sovaldi in combination with peginterferon alfa and ribavirin were fatigue, headache, nausea, insomnia and anemia.¹⁹

Ribavirin

The hemolytic anemia associated with ribavirin therapy may result in worsening of cardiac disease that has led to fatal and nonfatal myocardial infarctions. Significant teratogenic and embryocidal effects have been demonstrated in all animal species exposed to ribavirin. Therefore, ribavirin therapy is contraindicated in women who are pregnant and in the male partners of women who are pregnant.²⁰

Epclusa

The most common adverse reactions (incidence greater than or equal to 10%, all grades) observed with treatment with Epclusa for 12 weeks are headache and fatigue. The most common adverse reactions (incidence greater than or equal to 10%, all grades) observed with treatment with Epclusa and ribavirin for 12 weeks in patients with decompensated cirrhosis are fatigue, anemia, nausea, headache, insomnia and diarrhea.

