This study will target lung transplant candidates that currently face challenges in receiving an HCV-negative transplant and have a substantial probability of health decline while on the waiting list. This could include several broad cohorts of patients, but particularly those with "low to medium" LAS scores (the scores used for waitlist priority), which would largely include patients with chronic obstructive pulmonary disease (COPD) and cystic fibrosis (CF), who in many scenarios derive the greatest benefit for lung transplantation. This is especially true for patients with CF, who are among the youngest lung transplant patients. Unlike the USHER study, this study will include pre-enrollment testing for hepatic fibrosis using a Fibroscan to ensure patients do not have significant underlying liver disease.

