6.2. Subject selection criteria

6.2.1. Inclusion criteria

- 18-67 years of age
- Obtained agreement for participation from the lung transplant team
- No evident contraindication to lung transplantation other than the underlying lung disorder
- Able to travel to the University of Pennsylvania for routine post-transplant visits and study visits for a minimum of 12 months after transplantation
- No active illicit substance abuse
- Women must agree to use birth control in accordance with Mycophenolate Risk Evaluation and Mitigation Strategy (REMS) following transplant due to the increased risk of birth defects and/or miscarriage
- Both men and women must agree to use at least one barrier method of birth control or remain abstinent following transplant due to risk of HCV transmission
- Inclusion criteria for treatment (not for entry as study patient) will include any detectable HCV RNA by week 4 post-lung transplantation
- Able to provide informed consent

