8.1.2. Screening

The following procedures and activities will be performed during the screening process, after the informed consent is signed:

- Review medical history
- Vital signs
- Physical exam
- Fibroscan
- Review current medications
- Labs/phlebotomy: hepatic function panel, HCV RNA, HBV DNA, and HIV antibody
 - HBV Core Antibody will be checked in patients during screening, if not checked previously.
- Serum chg. pregnancy test (for women of childbearing potential)
- Completion of health status questionnaire (RAND-36)
- Provide instructions on recording of new medications and dose changes

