8.1.3.3. Visit 1: Post-Lung Transplant (between days 2 - 7)

The study staff will meet the subject in their HUP hospital room, three days after their lung transplant.

Initiating antiviral treatment

Treatment with the study drug will begin when the patient has a detectable and quantifiable HCV RNA post-transplantation and the donor and/or recipient have had an HCV genotype ascertained to guide treatment. As appropriate, subjects being discharged will be provided with a sufficient supply of the study drug.

As with any scientific protocol, safety will be considered before treating the patients. The treating physician will evaluate the patient's overall condition and make a judgment on whether initiating treatment is safe.

The following research procedures and activities will be performed:

- Assess for Adverse Events
- Obtain medication data
- Research Phlebotomy, including the NS5A drug resistance assay testing as appropriate (See Section 8.2.1 for complete list)
- Dispense study drugs

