8.2. Study schedule of procedures

8.2.1. Visits, lab testing, and other clinical testing

See next page for table.

Transplanting HCV Lungs into HCV Negative Lung Recipients

Protocol V5.0, November 2020

Week(s) post-KT		Day(s) post-KT		Visit Schedule		Research Visit Activities					Research Labs					Standard of Care								
Week(s) post-KT	Day(s) post-KT	Visit	Study Visits	Lab-Only	Informed Consent	Assess Adverse Events	Current Medications	Fibroscan	RAND-36 Questionnaire	HBV DNA HIV AB & LFTs	HBV Core Antibody	Urine Preg Test	Urine Protein/Cre Ratio	HCV RNA	Viral Kinetics (optional)♦	NSSA Resistance**	Genotyping of donor and/or recipient	Vitals & Physical Exam	Surveillance biopsy	CMP*	CBC	Tacrolimus		
Screening					✓	✓	✓	✓	✓	✓	✓	✓	✓	✓				✓						
1 (Begin treatment)	Day 2 - 7	V1	✓			✓	✓				✓■			✓	✓	✓	✓	✓	✓	✓	✓	✓		
1	7 ± 1 day			✓			✓							✓	✓					✓	✓	✓	✓	
2	10 ± 1 day	V2	✓			✓	✓							✓	✓				✓	✓	✓	✓	✓	
2	14 ± 1 day			✓			✓							✓	✓				¥	✓	✓	✓	✓	
3	21 ± 3 day	V3	✓			✓	✓							✓	✓				✓	✓	✓	✓	✓	
4	28 ± 3 day	V4	✓			✓	✓	✓	✓					✓	✓	✓			✓	✓	✓	✓	✓	
6	42 ± 7 day	V5	✓			✓	✓				✓■			✓	✓				✓	✓	✓	✓	✓	
8	56 ± 7 day	V6	✓			✓	✓							✓	✓				✓	✓	✓	✓	✓	
10	70 ± 7 day	V7	✓			✓	✓								✓				✓	✓	✓	✓	✓	
12	84 ± 7 day	V8	✓			✓	✓				✓■			✓	✓	✓			✓	✓	✓	✓	✓	
13 (End treatment)†	91 ± 7 day			✓			✓								✓									
16 (SVR 4)†	112 ± 14 day	V9	✓†			✓	✓							✓	✓			✓†	✓	✓	✓	✓	✓	
20 (SVR 8)	140 ± 7 day			✓										✓	✓				✓	✓	✓	✓	✓	
24 (SVR 12)	168 ± 14 day	V10	✓			✓		✓	✓					✓	✓	✓			✓	✓	✓	✓	✓	
28†	196 ± 7 day			✓											✓					✓	✓	✓	✓	✓
32	224 ± 7 day			✓											✓					✓	✓	✓	✓	✓
36 (SVR 24)	252 ± 7 day			✓										✓	✓	✓			✓	✓	✓	✓	✓	
40	280 ± 14 day			✓										✓					✓	✓	✓	✓	✓	
52	365 ± 14 day	V11	✓			✓		✓	✓					✓	✓	✓			✓	✓	✓	✓	✓	

* CMP=comprehensive metabolic panel which includes basic metabolic panel and liver function tests
care blood draw

** As appropriate ♦Viral Kinetics testing can be done anytime there is a standard of

[†]If patients require the 16 weeks of therapy, the last 4 weeks would be the same as weeks 9-12 of therapy [■]Only if HBV Core Antibodies are positive.

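### Fetal risk is called small because all participants will be over 40, yet eligibility starts at 18, and no pregnancy test is tied to the first dose or to ribavirin

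*Combined protocol and SAP*

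**What the plan says.** The Zepatier paragraph of section 12.11.4 acknowledges a risk of fetal harm and then discounts it: "Due to the age of the participants, this is a small risk, as all will be over 40 and unlikely to become pregnant". It goes on to safeguards that do not depend on age: "all pre-menopausal women with a uterus will be screened for pregnancy before enrollment", together with highly effective contraception as the Mycophenolate REMS defines it. The ribavirin paragraph of the same section reports malformations and embryo loss across the animal species tested and states that "ribavirin therapy is contraindicated in women who are pregnant".

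The synopsis and section 6.2.1 set the age range at "18-67 years of age". Section 4.1 singles out "patients with CF, who are among the youngest lung transplant patients" among those expected to benefit most.

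On testing, section 8.1.2 lists "Serum chg. pregnancy test (for women of childbearing potential" at screening. The schedule in section 8.2.1 has a column headed "Urine Preg Test". The laboratory item for Visit 1, where treatment may begin, reads "Research Phlebotomy, including the NS5A drug resistance assay testing as appropriate (See Section 8.2.1 for complete list". Section 12.4.3 provides for blood and urine pregnancy tests where appropriate, by reference to the schedule, and gives no time points. Pregnancy is an exclusion (section 6.2.2) and a reason to stop Zepatier or Epclusa (section 12.9).

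**The concern.** Two things are wrong, and the first hides the second.

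The protocol gives participants' age as its reason for rating fetal risk small, and that reason contradicts its own eligibility criteria. Study staff and the IRB would read it as a description of the people being enrolled.

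If participants may be of childbearing age, the timing of pregnancy tests matters, and no test is tied to the start of treatment. The exclusion and the stopping rule both depend on a pregnancy being known, and neither is linked to a test at dosing. The main stake is ribavirin. For Zepatier alone the stake is lower, since section 12.9 reports no embryo-fetal effects in rats or rabbits. This is a participant-safety and consistency point; it does not touch the SVR-12 analysis.

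**Working it through.** No sample-size or error-rate formula applies, so the check sets the relevant places side by side and counts.

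**1. Age.** The stated lower bound is over 40 (section 12.11.4). The eligibility bound is 18 (synopsis and section 6.2.1), and no other section raises it. The protocol therefore admits ages 18 to 40, which section 12.11.4 treats as absent. In whole years that is 40 − 18 + 1 = 23 of 67 − 18 + 1 = 50, or 46% of the permitted range. This is a share of the range, not of patients; the protocol gives no expected age or sex mix.

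**2. The schedule in section 8.2.1.** The table has 23 column headers, and the pregnancy test is column 13.

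| Row | Marked columns | Column 13 |
|---|---|---|
| Screening | 6–15 and 19 | marked |
| Visit 1 (treatment start) | 4, 7, 8, 12 and 15–23 | blank |

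Both rows fit the 23 headers. The next row (day 7) carries a mark in a 24th position, so the later rows are out of alignment in the text available to me. I saw no later mark in column 13, but the conclusion does not rest on those rows.

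**3. Visit procedure lists.** There are nine: section 8.1.2 and sections 8.1.3.3 to 8.1.3.10. A pregnancy test is named in one, section 8.1.2. The eight post-transplant lists refer to section 8.2.1 for laboratory work, so their silence is supporting evidence only.

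**4. Interval from the last clearly required test to the first dose.** This is waiting-list time (section 6.1, no limit stated) plus up to about 4 weeks after transplant (section 7.1.2). It has no upper bound in the plan. The birth-control criteria in section 6.2.1 apply after transplant, and the contraception instruction in section 12.11.4 has no start date, so the waiting-list period is not clearly covered by contraception either.

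**5. Ribavirin.**

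| Use | Where | Test named beforehand | Other precaution |
|---|---|---|---|
| First line, with NS5A polymorphisms | 7.1, 8.1.3.3.1 | NS5A resistance | two contraceptive methods |
| Second line, after failure | 7.1.5, 8.1.3.11 | NS5A resistance | two contraceptive methods (7.1.2) |

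Neither entry names a pregnancy test. Second-line treatment repeats the study visits, but that adds a test only if the post-transplant schedule contains one.

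**6. Size.** Women affected: 0 to 11, since 11 are to be treated. Added tests if one is required before the first dose, before first-line ribavirin and before second-line ribavirin: at most 11 × 3 = 33, so the range is 0 to 33.

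**The case against.** The strongest reply has five parts.

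- **The age sentence drives no procedure.** Testing and contraception apply to all pre-menopausal women whatever their age, so no younger woman is exempted. That is correct, and taken alone the sentence needs only a wording correction. It does not answer the timing gap.
- **A test does precede the first dose, namely the screening test.** True. The defect is that nothing is repeated after a waiting period of unstated length.
- **The waiting list is monitored.** Section 12.8.3 requires monthly record review and patient contact every 6 to 8 weeks to pick up new exclusions, section 6.1 re-reviews eligibility on reactivation, and section 8.1.3.3 asks the physician to judge whether starting treatment is safe. Section 8.1.3.2 also allows extra safety laboratory tests. These reduce the risk and permit a test; none requires one.
- **Ribavirin exposure will be rare.** First-line use needs genotype 1a or genotype 1 of unknown subtype, specified polymorphisms and clinician discretion. Second-line use under section 7.1.5 needs failure of Zepatier: at the 94–100% success the protocol cites, 11 × (1 − 0.94) = 0.66 down to 0 expected failures, in either sex. This stands, and it limits the expected number of exposures. It does not justify omitting a simple check before a contraindicated drug.
- **Absence is hard to prove here.** Later schedule rows are misaligned, the REMS content is not in the protocol, and a part of the document between sections 6.1 and 6.2 was not available to me. Later urine testing therefore cannot be ruled out. The age contradiction and the blank Visit 1 cell do not depend on any of this.

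**Conclusion.** The concern holds. The over-40 statement is false against the protocol's own criteria. The only pregnancy test the plan clearly requires comes before a waiting period with no stated limit. At Visit 1 the schedule cell is blank, and no text ties a test to the first antiviral dose or to either use of ribavirin.

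The number of women affected lies between 0 and 11 and is probably small. The consequence for any one of them could be serious, chiefly through ribavirin. The correction should be made, although it has no bearing on the efficacy results.

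Confidence is high on the age statement, the Visit 1 row and the visit text. It is lower on the schedule rows after Visit 1, which would matter for a woman whose first dose falls later. The verdict assumes that no testing requirement sits in the REMS or in the part of the protocol I could not see.

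**What to change.** 1. In section 12.11.4, delete the clause about all participants being over 40. Restate fetal risk for women of childbearing potential aged 18 to 67, mentioning cystic fibrosis patients.
2. Require a pregnancy test in these women before the first antiviral dose, whenever that falls between Visit 1 and week 4, and before any first- or second-line ribavirin course.
3. Mark these tests in section 8.2.1 by a footnote linked to the dose, not to a fixed visit. Leave further on-treatment testing to the investigators.
4. As a clerical correction, point section 12.4.3 to section 8.2.1 instead of section 5.2, which holds the specific aims.

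Section 12.11.4 also bars ribavirin in men whose partners are pregnant, so a question on partner pregnancy before ribavirin would fit at the same point.

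The cost is a wording change, a footnote and 0 to 33 inexpensive tests at visits that already take place. The true number should be well below 33, because not all 11 will be women of childbearing potential and few will need ribavirin. Whether the consent form must change cannot be judged, because its pages were not available to me.
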